4.2 Inclusion Criteria

Participants must meet *all* the following criteria to be eligible for the study:

1. Adult males or females aged ≥ 18 to ≤ 65 years at screening
2. Body Mass Index $\leq 30 \text{ kg/m}^2$
3. Able to provide informed consent indicating they understand the purpose of, and procedures required, for the study and are willing to participate
4. If female, willing not to become pregnant up to 8 weeks after last dose of study vaccine, not breast feeding
5. If female: Not pregnant and one of the following:
 - Of non-childbearing potential (i.e. women who have had a hysterectomy or tubal ligation or are post-menopausal, as defined by no menses in ≥ 1 year)
 - Sexual abstinence, only if the participant refrains from heterosexual intercourse during the entire study period and it is the usual lifestyle of the participant
 - Of childbearing potential but agrees to practice highly effective contraception for 4 weeks prior to study vaccine and 8 weeks after study vaccine. Highly effective methods of contraception include one or more of the following:
 - Male partner who is sterile (medically effective vasectomy) prior to the female participant's entry into the study and is the sole sexual partner for the female participant
 - Combined (estrogen and progestogen containing) hormonal contraception associated with inhibition of ovulation:
 - oral
 - intravaginal

- transdermal
- Progestogen-only hormonal contraception associated with inhibition of ovulation:
 - oral
 - injectable
 - implantable
 - An intrauterine device
 - Bilateral tubal occlusion

Healthy participants (cohorts 1 and 2):

6. Considered to be healthy with no current conditions that may significantly impair participant safety or influence study results, in the opinion of the Investigator

Participants with well controlled CHB (cohorts 3 and 4):

7. Documented evidence of chronic HBV infection (e.g. HBsAg positive ≥ 6 months with detectable HBsAg levels at screening)
8. Receipt of only either entecavir or tenofovir for at least 12 months before screening
9. Virally suppressed (HBV DNA <40 IU/mL for ≥ 6 months)
10. HBsAg <10000 IU/mL

Healthy participants (cohort 5):

11. Considered to be healthy with no current conditions that may significantly impair participant safety or influence study results, in the opinion of the Investigator
12. Adult males or females aged ≥ 40 to ≤ 60 years at screening
13. Completed second dose of COVID-19 AZD1222 vaccine 10 to 18 weeks before enrolment

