10. PLANNED STATISTICAL METHODS

10.1. Statistical Considerations

10.1.1. General definitions

Definition of baseline

Baseline is defined as the last non-missing value for a participant, for the particular parameter, that is prior to the administration of study vaccine.

Study completion definition

A participant completes the study by engaging in study activities up to and including the End of Study Visit at Day 168 (+/- 7 days), for cohorts 1 to 4, and Day 84 (+/- 7 days) for cohorts 5 and 6.

Treatment Group

There are six treatment groups in this study; the Healthy Participants and CHB participants are split into high and low doses of vaccination. Healthy participants in the high dose group are further split into those with no previous exposure to ChAdOx1 vectored vaccines, those with recent previous exposure to Covid-19 ChAdOx1 vectored vaccine (cohort 5) and those with previous exposure to Covid-19 mRNA based vaccines (cohort 6).

Results below limit of detection and quantification

Immunogenicity results that are below the limit of quantification or detection (i.e. reported as <X or BLQ) will be replaced by 0 for any summaries but will be listed as reported.

Geometric Mean and Standard Deviation

The geometric mean (GM) and geometric standard deviation (GSD) are obtained by calculating the mean and SD of the log-transformed data and back-transforming these. If there are any zero values in the data a small number should be added to all values before log-transformation and then subtracted from the resulting GM. This small number will be 1 unless stated otherwise.

GM = antilog (mean (log(value + S))) – S, where S is a small number, relative to the non-zero results.

GSD = antilog(standard deviation(log(value + S)))

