For CHB participants only (expected number of participants is 12), the reduction of hepatitis B DNA levels is assessed by subtracting the DNA levels at each follow-up visit (Day 28, Day 56, Day 84 and Day 168) from the DNA levels pre vaccination (Day 0). In addition, the maximum reduction (at any timepoint) will be calculated. The hepatitis B DNA levels will be log transformed (base 10) prior to any calculations, and summaries will be presented on the log-scale.

Total T cell response to the antigens encoded by ChAdOx1-HBV as measured in a peptide-stimulated ELISpot assay

Assessment of immune response by ELISpot assay will be based on the number of IFN- γ spot-forming units (SFU) per 10^6 PBMC in response to stimulation with each antigenic peptide pool. Responses are background (DMSO)-subtracted and will be summarized by the following combinations of stimulation conditions: Core, Pol1-Pol4, Pre S1/S2/S, and Sli.

Background-subtracted results that do not exceed a positivity threshold of 25 will be set to 0. Background-subtraction resulting in negative values will be set to 0.

Background-subtracted ELISpot responses at each immunology timepoint and their changes from baseline will be summarized by treatment group and combination of stimulation antigens. ELISpot results will also be listed.

Role of recent previous exposure to a different ChAdOx1 vectored vaccine (cohorts 5 and 6)

For participants in cohorts 5 and 6 the anti-vector immunity is assessed by a multi-parameter index made of CD4+ magnitude and CD8+ magnitude (see above) and by the titre of anti-vector neutralising antibodies.

T cell responses will be background-subtracted and presented in listings. Negative, background-subtracted responses will be set to 0.

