The denominator is the number of participants with non-missing data at baseline and follow-up.

Table 14.2.3
Reduction in Hepatitis B DNA levels in CHB Participants
Immunogenicity Analysis Set

Hepatitis B DNA (log ₁₀ copies/ml)	Low Dose (N=xx)			High Dose (N=xx)			Total (N=xx)		
	Absolute		Change	Absolute		Change	Absolute		Change
	CHB Participants			CHB Participants			CHB Participants		
Baseline	n	xx		xx	xx		xx	xx	
	Mean	xx, x		xx, x	xx, x		xx, x	xx, x	
	SD	xx, xx		xx, xx	xx, xx		xx, xx	xx, xx	
	Median	xx, x		xx, x	xx, x		xx, x	xx, x	
	Min, Max	xx, xx		xx, xx	xx, xx		xx, xx	xx, xx	
Day 28	n	xx		xx	xx		xx	xx	
	Mean	xx, x		xx, x	xx, x		xx, x	xx, x	
	SD	xx, xx		xx, xx	xx, xx		xx, xx	xx, xx	
	Median	xx, x		xx, x	xx, x		xx, x	xx, x	
	Min, Max	xx, xx		xx, xx	xx, xx		xx, xx	xx, xx	
Day 56	n	xx		xx	xx		xx	xx	
	Mean	xx, x		xx, x	xx, x		xx, x	xx, x	
	SD	xx, xx		xx, xx	xx, xx		xx, xx	xx, xx	
	Median	xx, x		xx, x	xx, x		xx, x	xx, x	
	Min, Max	xx, xx		xx, xx	xx, xx		xx, xx	xx, xx	
Day 84	n	xx		xx	xx		xx	xx	
	Mean	xx, x		xx, x	xx, x		xx, x	xx, x	
	SD	xx, xx		xx, xx	xx, xx		xx, xx	xx, xx	
	Median	xx, x		xx, x	xx, x		xx, x	xx, x	
	Min, Max	xx, xx		xx, xx	xx, xx		xx, xx	xx, xx	
Day 168	n	xx		xx	xx		xx	xx	
	Mean	xx, x		xx, x	xx, x		xx, x	xx, x	
	SD	xx, xx		xx, xx	xx, xx		xx, xx	xx, xx	
	Median	xx, x		xx, x	xx, x		xx, x	xx, x	
	Min, Max	xx, xx		xx, xx	xx, xx		xx, xx	xx, xx	
Maximum Change	n	xx		xx	xx		xx	xx	
	Mean	xx, x		xx, x	xx, x		xx, x	xx, x	
	SD	xx, xx		xx, xx	xx, xx		xx, xx	xx, xx	
	Median	xx, x		xx, x	xx, x		xx, x	xx, x	
	Min, Max	xx, xx		xx, xx	xx, xx		xx, xx	xx, xx	

Change in hepatitis B DNA levels is defined by subtracting the DNA levels at each follow-up visit (Day 28, Day 56, Day 84 and Day 168) from the DNA levels pre vaccination (Day 0). A positive change is equivalent to a reduction in DNA levels.
The denominator is the number of participants in the analysis set.

Programming Note: The data may be provided as copies/ml - this should be transformed to log10 copies/ml before summarising

Table 14.2.4
Background-subtracted T-Cell response (ELISpot)
Immunogenicity Analysis Set

Stimulation Antigen Visit	Healthy Participants						Healthy Participants Covid-19 Vaccinated						Total (N=xx)			
	Low Dose (N=xx)			High Dose (N=xx)			ChAdOx1 (N=xx)			mRNA (N=xx)			Absolute Change		Absolute Change	
	Absolute	Change	Absolute	Absolute	Change	Absolute	Absolute	Change	Absolute	Change	Absolute	Change	Absolute	Change	Absolute	Change

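### The Maximum Change row for HBV DNA in SAP Table 14.2.3 takes the best of four visits per participant, so its mean is biased towards a reduction when nothing has changed

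*SAP*

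**What the plan says.** SAP 10.7.2 derives the change in HBV DNA by subtracting the level "at each follow-up visit (Day 28, Day 56, Day 84 and Day 168) from the DNA levels pre vaccination (Day 0"), after a log10 transformation: "The hepatitis B DNA levels will be log transformed (base 10) prior to any calculations". It then adds one further summary: "In addition, the maximum reduction (at any timepoint) will be calculated".

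In the shell of Table 14.2.3 (SAP section 14) this is the last block, labelled "Maximum Change", with n, mean, SD, median, minimum and maximum by dose and in total. The footnote fixes the sign: "A positive change is equivalent to a reduction in DNA levels". The table has no block for the largest increase.

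Two other provisions bear on the row. Protocol 4.2 admits CHB participants only if "Virally suppressed (HBV DNA <40 IU/mL for" at least six months. SAP 10.1.1 says that results below the limit ("i.e. reported as <X or BLQ) will be replaced by 0 for any summaries"), and the opening line of 10.7.2 repeats the rule. HBV DNA is analysed under the immunogenicity heading, so I read the rule as covering it. An offset of 1 before taking logs is given in 10.1.1 only for the geometric mean and geometric SD.

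**The concern.** The row selects, for each participant, the most favourable of four noisy differences and then averages those selections. Noise alone pushes such an average in the favourable direction. Cohorts 3 and 4 are both vaccinated (SAP 6.2, Table 1), so no comparison group shows how large the row would be without a vaccine effect. No maximum rise is printed to show that the noise runs both ways.

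HBV DNA reduction is a secondary endpoint, and Protocol 3.2 says that hepatitis B biomarkers will help to assess potential efficacy. A positive mean in this row could therefore be taken for a small antiviral effect. The row is not needed for the endpoint: the protocol does not mention a maximum, and the parallel HBsAg table (14.2.1) has no such row.

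**Working it through.** The documents state no figure for this row, so there is nothing to reproduce. The question is what the row would show with no effect.

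**Inputs from the documents.** One Day 0 value B and four follow-up values F1 to F4 per participant; log10 scale; positive means reduction; 6 CHB participants per dose; entry below 40 IU/mL; results below the limit set to 0.

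**Inputs not in the documents, so assumed.** Within-person SD of log10 HBV DNA, and the assay limit.

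**Case 1: all values quantifiable, no effect, five independent values with the same mean and SD.**

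- Participant score: M = max(B − Fk) = B − min(F1..F4).
- The mean of the largest of four standard normals is ∫ x·4·φ(x)·Φ(x)³ dx = 1.029, and the smallest is its mirror image. So E[M] = 1.029 × SD.
- SD 0.1: 0.10 log10, an apparent fall of 1 − 10^(−0.103) = 21%. SD 0.2: 0.21 log10, 38%. SD 0.3: 0.31 log10, 51%.
- M is negative only when Day 0 is the lowest of the five values, so P(M > 0) = 1 − 1/5 = 0.80.
- P(all 6 in a cohort positive) = 0.8^6 = 0.26. P(all 12 positive) = 0.8^12 = 0.07.
- Simulation (1,000,000 participants): the mean of 6 is above zero with probability 0.98, and the mean of 12 with probability 0.998. The four visit-specific mean changes are 0.00.

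Missing visits are not imputed (SAP 10.1.4), so the no-effect value also depends on attendance: 0, 0.56, 0.85 or 1.03 SDs for one, two, three or four follow-up visits.

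**Case 2: the SAP's rule for results below the limit.** Assumptions: screening value below 40 IU/mL; limit 10 or 20 IU/mL; results below it set to 0; log10(value + 1); between-person SD 0.3. A participant below the limit at Day 0 has B = 0 and every F ≥ 0, so M ≤ 0, and M = 0 exactly if any follow-up is also below the limit. Simulated results with no effect, for within-person SD 0.2 / 0.3:

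| Limit (IU/mL) | Mean log10 level | Below limit at Day 0 | Share with M > 0 | Mean of M (log10) |
|---|---|---|---|---|
| 10 | 0.3 | 0.97 / 0.95 | 0.026 / 0.049 | 0.027 / 0.056 |
| 10 | 0.7 | 0.80 / 0.77 | 0.188 / 0.225 | 0.174 / 0.246 |
| 10 | 1.0 | 0.52 / 0.53 | 0.436 / 0.444 | 0.332 / 0.430 |
| 10 | 1.3 | 0.25 / 0.29 | 0.651 / 0.637 | 0.371 / 0.512 |
| 20 | 0.3 | 1.00 / 0.99 | 0.003 / 0.009 | 0.004 / 0.013 |
| 20 | 0.7 | 0.96 / 0.93 | 0.043 / 0.072 | 0.057 / 0.103 |
| 20 | 1.0 | 0.83 / 0.79 | 0.167 / 0.204 | 0.201 / 0.278 |
| 20 | 1.3 | 0.60 / 0.58 | 0.375 / 0.400 | 0.392 / 0.495 |

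The mean runs from 0.004 to 0.51 log10. It is below the Case 1 value for the same SD (0.21 or 0.31) in the runs with 77% or more below the limit at Day 0. It is above that value in the runs with 25% to 60%, because one dip below the limit is scored as a fall to zero. For example, 15 IU/mL falling once below the limit scores log10(16) = 1.20, which adds 1.20/6 = 0.20 to a cohort mean. Visit-specific mean changes again stay at 0.00 to two decimals.

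**The case against.** The strongest reply is that these participants are already suppressed. Anyone below the limit at Day 0 cannot score above 0 under the SAP's own rule, and if all 12 were below it the row would show zero or a rise. This stands. It means that the size of the bias cannot be known from the documents, and that the low entry level is not in itself a reason to expect a large positive row.

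A reader might infer more than the documents support, in three ways:

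- **That the row is positive by construction.** It is not. Even with every value quantifiable, 20% of individual scores are negative. It is the mean that is biased.
- **That Table 14.2.3 as a whole would show a reduction with no effect.** Only the last block is affected. The Day 28, 56, 84 and 168 change rows involve no selection.
- **That the table hides HBV DNA becoming detectable again.** The minimum of each visit's change is the largest rise, the maximum of each absolute column is the highest level, and Listing 16.2.6.2 gives HBV DNA by participant and visit, with below-limit results listed as reported. With 12 participants, a rise can be read directly.

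It is also fair to say that no formal testing is planned (SAP 10.1.3) and that no threshold or decision rule attaches to the row. That limits the harm, but does not make the mean interpretable.

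**Conclusion.** The point holds for one row. With no effect, the expected score is the expected Day 0 value minus the expected lowest follow-up value, which cannot be negative if Day 0 and follow-up values share one distribution. The error therefore runs in one direction only. Its size is about 1.03 within-person SDs if all values are quantifiable: 0.10 to 0.31 log10 for SDs of 0.1 to 0.3. Under the below-limit rule it ranged from 0.004 to 0.51 log10 in the runs shown, and is near zero when almost all participants are below the limit at Day 0. These sizes rest on assumed SDs, levels and limits, on independent errors between visits, and in the second case on an offset of 1 in IU/mL.

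A related gap is that the SAP sets below-limit results to 0 and then takes log10, without saying how for HBV DNA. That affects every row of the table. The overall importance is minor: a supplementary descriptive row for a secondary endpoint.

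**What to change.** In SAP 10.7.2 and Table 14.2.3, either drop the Maximum Change block or print the maximum increase from baseline beside it. If the block stays, add a footnote that it takes the most favourable visit and is not evidence of reduction.

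State in 10.7.2 how an HBV DNA result set to 0 is log10-transformed, and in which unit. The table is headed in copies/ml while eligibility is in IU/mL, and adding 1 does not mean the same thing in both.

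Optionally, add counts by visit and dose of HBV DNA not detected, detected below quantification, and quantifiable.

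The cost is an edit to the text and one table shell. It needs no new data, and the visit-specific rows keep the information that the endpoint requires.

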10.7.3. Exploratory Efficacy Analysis

The following exploratory efficacy endpoints will be analysed separately from this SAP and will be an appendix to the Clinical Study Report. Any data collected within the study database will be listed:

- Effect on serum hepatitis B core related antigen (HBcAg)
- Effect on serum hepatitis B circulating pre genomic ribonucleic acid (pgRNA)
- Liver fine needle aspirate (LFNA) assays will be used to quantify and characterise intrahepatic immune and parenchymal cells and/or HBV DNA and RNA transcripts.
- Effect of prior AZD1222 on the CD4+ and CD8+ T cell magnitude and phenotype as measured by multiparameter flow cytometry

10.8. Safety Analysis

All analyses of safety endpoints will be descriptive. The safety analysis set will be used for all safety presentations. No statistical analysis of safety data will be performed.

10.8.1. Adverse Events and Serious Adverse Events

All adverse events will be coded using MedDRA, Version 22.1.

An adverse event is treatment emergent if the onset date is on or after the date of vaccination. Should any onset date for an adverse event be missing or only a partial date recorded (such that it cannot be determined if the event onset was prior to start of study treatment or not) then it will be assumed that the event is treatment emergent, unless the adverse event stop date indicates otherwise. Any adverse event with an onset date earlier than the date of vaccination will be classified as a pre-treatment adverse event. Time is not collected and will not be used in the identification of treatment emergent AEs.

If a participant experiences more than one AE with the same preferred term, that preferred term will be counted only once. It will be assigned the greatest observed severity and the strongest relationship to study treatment among those events for the tables in which those characteristics are summarised.

Treatment-emergent AEs will be summarised by:

- Treatment group, system organ class, and preferred term;
- Treatment group, system organ class, preferred term and severity;
- Treatment group, system organ class, preferred term and severity for only those events that are judged to be related to study treatment;

Treatment-emergent vaccine-related (i.e. where “related” = Yes) AEs will be summarised by:

- Treatment group, system organ class, preferred term;

Treatment-emergent adverse events of special interest, where events of special interest will be noted in the database, will be reported by:

- Treatment group, system organ class, and preferred term;

A summary table of adverse event incidence will also be presented by treatment group and overall to include the number and percentage of participants with at least one: TEAE, TEAE severity (Grade 1 to 5 separately, and additionally those subjects with a Grade 3, 4 or 5), vaccine related TEAE, vaccine related severity (Grade 1 to 5 separately, and additionally those subjects with a Grade 3, 4 or 5), SAE, vaccine related SAE, TEAE leading to withdrawal from the study.

Note: ‘Adverse Event Leading to Discontinuation from the Study’ will be those Participants that withdrew from the study due to an adverse event.

Serious adverse events and adverse events directly resulting in withdrawal from study will be listed by treatment group.

In all AE summary tables results will be displayed ordered in terms of decreasing frequency of SOC occurrence (based on total across treatment groups), and within each SOC also ordered in terms of decreasing frequency of preferred term occurrence (also based on total across treatment groups). In all AE summary tables, in addition to presenting the information by treatment group, a total column (treatment groups combined) will also be presented.

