3.1.2 *Study Methodology*

Participants will be screened in the period Day -42 to Day -1. Informed consent will be obtained before any study specific procedures are performed. Eligible participants will then attend the clinic to receive study vaccine on Day 0. Participants will be enrolled sequentially.

The study will investigate response to study vaccine as shown in [Table 2](#). On Day 0, an electronic diary (eDiary), tape measure and thermometer will be provided to perform self-assessment of local and systemic reactogenicity. All participants will then have a follow-up telephone call on Day 1 and return to the clinic for study assessments on Days 7, 14, 28, 84. Participants in cohorts 1-4 only, will also have follow up visits on Day 56 and Day 168. End of study visit procedures will be performed at the final visit.

Five healthy participants will be administered the low dose first (cohort 1). Dose escalation will only be initiated in the next 5 healthy participants (cohort 2) following SMC review.

Six CHB participants will be administered the low dose (cohort 3) before the dose escalation is initiated in the remaining 6 CHB participants (cohort 4).

Thirty healthy participants (15 who have received two doses of AZD1222 [cohort 5] and 15 who have received at least two doses of either Pfizer or Moderna mRNA COVID-19 vaccine [cohort 6]) will be dosed in parallel with the high dose used in cohorts 2 and 4.

The first participant in each of cohorts 1-4 will be assessed for 1 hour in the clinic post-vaccination in case of immediate adverse events (timed after the end of study vaccine administration). All other participants will be assessed for 30 minutes.

The safety and immunogenicity assessments to be performed in cohorts 1-4 are:

- Haematology (full blood count, haemoglobin, haematocrit, erythrocytes, mean cell volume, mean corpuscular haemoglobin, mean corpuscular haemoglobin concentration, leukocytes, neutrophils, lymphocytes, monocytes, eosinophils, basophils, fibrinogen, prothrombin time [PT] and international normalised ratio [INR], activated partial thromboplastin time [aPTT] and platelets) will be analysed at screening, pre-vaccination on Day 0 and on Days 7, 14, 28, 56, 84 and 168
- Biochemistry (sodium, potassium, urea, creatinine and albumin) will be analysed at screening, pre-vaccination on Day 0 and on Days 7, 14, 28, 56, 84 and 168

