The reporting period for all adverse events begins on the date the informed consent is signed. Solicited adverse events are recorded in the eDiary up to 3 days post-vaccination. All other events are recorded in the eCRF up until Day 28. All SAEs and or Adverse events of special interest are recorded until at least 168 days after the last study vaccination dose and for all serious or study vaccine-related adverse events until these are resolved or until participant contact discontinues.

Adverse event information will be collected at study visits and participant will be instructed to call study team members to report any abnormalities during the intervals between study visits and to come to the study centre if medical evaluation is needed and the urgency of the situation permits.

8.2.3 *Recording and Assessment of Adverse Events by the Investigator*

Solicited adverse events are recorded in the eDiary up to 3 days post-vaccination. All other adverse events are recorded in the eCRF up to until Day 28. All adverse events, both those observed by study team members and those spontaneously reported by the participant, will be recorded in the eCRF. Solicited adverse events will be reported using pre-defined terms. Unsolicited adverse events will be reported using a recognised medical term or diagnosis that accurately reflects the event.

Adverse events will be assessed by the Investigator, or a medically qualified study team member, for severity, relationship to study vaccine, action taken, outcome and whether the event meets criteria as an SAE according to the following guidelines:

8.2.3.1 *Assessment of Severity*

The severity of adverse events will be graded according to the toxicity table in [Appendix 1](#). The scale shown in [Table 3](#) will be used to assess severity of adverse events not listed in [Appendix 1](#).

Table 3 Severity Grading of Adverse Events not listed in the Toxicity Table for Clinical and Laboratory Abnormalities

Grade	Severity	
1	Mild	Asymptomatic or mild symptoms; clinical or diagnostic observations only; or intervention not indicated; no disruption of normal daily activity.
2	Moderate	Minimal, local, or non-invasive intervention indicated; discomfort sufficient to reduce or affect daily activity.
3	Severe	Severe or medically significant, but not immediately life-threatening; hospitalisation or prolongation of hospitalisation indicated; inability to work or perform normal daily activity.

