4	Life-threatening	Represents an immediate threat to life.
5	Fatal	Death as a result of this adverse event

A change in severity of an adverse event will not be recorded as a new adverse event. Only the highest severity level that occurs during the entire period of the adverse event will be recorded on the eCRF with the onset and resolution dates encompassing the entire duration of the event.

Note: It is important to distinguish between serious and severe adverse events. Severity is a measure of intensity whereas seriousness is defined by the criteria in [Section 8.2.1.3](#).

 8.2.3.2 *Assessment of Relationship*

Solicited adverse events of vaccination site reactions will be considered causally related to study vaccine.

For all other adverse events, the Investigator will determine a **causal relationship** to the study vaccine. A number of factors will be considered in making this assessment, including: 1) the temporal relationship of the event to the administration of the study vaccine 2) whether an alternative aetiology has been identified and 3) biological plausibility.

Causality of all adverse events should be assessed by the Investigator using the following question:

“Is there a reasonable possibility that the adverse event may have been caused by the study vaccine?”

- YES (related): There is a reasonable possibility that the study vaccine contributed to the adverse event
- NO (not related): There is no reasonable possibility that the adverse event is causally related to the administration of the study vaccine. There are other, more likely causes and administration of the study vaccine is not suspected to have contributed to the adverse event

The Investigator determines causality. The Sponsor and LMM can add another causality assessment to the Investigator's causality assessment. The causality assessment given by the Investigator must not be downgraded by the Sponsor. If the Sponsor disagrees with the

Investigator's causality assessment, the opinion of both the Investigator and the Sponsor should be provided with the report.

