8.2.5 Follow-up of Participants after Adverse Events

8.2.5.1 *Investigator Follow-up*

Treatment of any adverse events will be determined by the Investigator using his/her best medical judgment and according to current clinical practice guidelines. All applied measures as well as follow-up will be recorded in the appropriate eCRF.

The Investigator will continue follow-up on adverse events, including laboratory abnormalities and solicited adverse events, until the event has resolved, is otherwise satisfactorily explained, or the participant completes the study. The resolution date will be recorded on the eCRF as the last date on which the participant experienced the adverse event. If an adverse event resolution date is uncertain the Investigator should estimate the completion date based on medical judgment and interview of the participant. Approximate dates of resolution from phone or other communications may be taken as adverse event resolution dates. Some examples of estimation of adverse event resolution are: 1) an asymptomatic laboratory abnormality on one visit that has not been followed-up between visits but has resolved by the next visit may be assumed to have resolved by the midpoint of the inter-visit interval; 2) A resolved adverse event that was treated may be assumed to have been resolved by the end of treatment.

Adverse events that are still present at the end of the study should be recorded as ongoing.

Information recorded on the eCRF must be substantiated in the source documents. If an adverse event evolves into a condition that becomes “serious,” it will be designated as serious on the adverse event eCRF and a supplemental SAE report form will be completed.

Follow-up for SAEs must continue until resolution and the outcome reported to the Sponsor, even if this extends beyond the SAE reporting period.

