All adverse events will be listed, including the verbatim description and MedDRA preferred terms and system organ class (SOC).

Treatment emergent adverse events (TEAEs) are defined as those occurring after the study vaccine administration.

TEAEs will be summarised by SOC and by preferred term. The incidence of TEAEs will be based on the numbers and percentages of participants with events and number of events. TEAEs will be further summarised by severity and relationship to study vaccine.

An overall summary of adverse event incidence will also be presented by study vaccine dose and overall to include the number and percentage of participants with at least one: TEAE, vaccine-related TEAE, Grade 3 to Grade 5 TEAE, death, SAE, vaccine-related SAE, AESI, vaccine-related AESI, TEAE leading to study vaccine discontinuation and TEAE leading to study discontinuation.

Narratives will be written for any deaths, other SAEs, AESIs, TEAEs leading to study vaccine discontinuation and TEAEs leading to study discontinuation.

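### An unsolicited adverse event recorded in screening that worsens after vaccination stays one record, is classed pre-treatment, and is missing from the main treatment-emergent AE tables

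*SAP*

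**What the plan says.** Four rules in the two documents meet on this point.

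- **Collection.** Protocol 8.2.2: "The reporting period for all adverse events begins on the date the informed consent is signed". Protocol 3.1.2: "Participants will be screened in the period Day -42 to Day -1".
- **Recording.** Protocol 8.2.3.1: "A change in severity of an adverse event will not be recorded as a new adverse event". On grading, the same section adds: "Only the highest severity level that occurs during the entire period of the adverse event will be recorded on the eCRF". The dates on that single entry run from first onset to final resolution.
- **Becoming serious.** Protocol 8.2.5.1, on an event that turns serious: "it will be designated as serious on the adverse event eCRF and a supplemental SAE report form will be completed". No new AE entry is called for.
- **Classification.** SAP 10.8.1: "Any adverse event with an onset date earlier than the date of vaccination will be classified as a pre-treatment adverse event". The footnotes to Tables 14.3.1.1, 14.3.1.2 and 14.3.1.4 carry the same onset-only rule. The protocol's own definition (10.2.2.6.1) is no wider: "Treatment emergent adverse events (TEAEs) are defined as those occurring after the study vaccine administration".

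Neither definition mentions worsening, and SAP Section 11 lists no change that deals with it.

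**The concern.** AE and SAE incidence is the primary endpoint of this first-in-human study (SAP 7.1), and the AE summary tables are restricted to treatment-emergent events. An event that is mild before the injection and severe afterwards is one that a safety reader would want counted. Under the recording rule it keeps its screening onset date, and under the classification rule that date alone removes it. The omission can only lower a treatment-emergent count.

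Such events are foreseeable. Screening can last six weeks, and CHB participants may have an optional liver aspirate during it, so some events may still be ongoing on Day 0.

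**Working it through.** No figure in the plan bears on this point and the safety analysis is descriptive (SAP 10.8), so there is nothing to reproduce. The check applies the rules in order to one record, then asks where that record appears.

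**Step 1: the record.** Take an unsolicited clinical event with onset on Day -10 at Grade 1 that reaches Grade 3 on Day +5. Under Protocol 8.2.3.1 it is stored once: onset Day -10, Grade 3. If it became serious on Day +5, the serious flag goes on the same entry (8.2.5.1). Day +5 is not held on the AE record as the date of the change.

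**Step 2: the flag.** SAP rule: treatment-emergent if onset day ≥ 0. Here -10 ≥ 0 is false, so the event is pre-treatment.

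**Step 3: where it appears.**

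| Output | Event shown? |
|---|---|
| Tables 14.3.1.2 and 14.3.1.4 (by term; by severity) | No |
| Table 14.3.1.3 (if of special interest) and 14.3.1.5 (if related) | No |
| Table 14.3.1.1: TEAE, severity, related-AE and AESI rows | No |
| Table 14.3.1.1: SAE and related-SAE rows | Unclear: the text of SAP 10.8.1 names these rows without a treatment-emergent qualifier, but the table title and footnote impose one |
| Table 14.3.1.1: withdrawal row | Yes, if the participant withdrew because of it, since the row is taken from the study completion page |
| Table 14.3.2.1 (SAE listing) | Yes, if serious, marked TE = No |
| Listing 16.2.7 (all AEs) | Yes, marked TE = No, with one grade and no date of worsening |

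**Step 4: what is captured by another route.** Solicited reactions on Days 0 to 3 are summarised by worst post-vaccination grade, whatever their onset (SAP 10.8.2). Graded laboratory and vital-sign values enter shift tables from baseline to maximum post-baseline grade (SAP 10.8.3, 10.8.4). That leaves unsolicited clinical events, and solicited-type symptoms that worsen after Day 3.

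**Step 5: weight of one participant.** Cohort sizes are from SAP Table 1. For a participant with no other event in the row, the change is 100 × 1/n:

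- n = 5 (cohorts 1 and 2): 100/5 = 20.0 percentage points
- n = 6 (cohorts 3 and 4): 100/6 = 16.7
- n = 15 (cohorts 5 and 6): 100/15 = 6.7
- n = 52 (all participants): 100/52 = 1.9

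**Step 6: the same record under a wider rule.** If emergence also covered a rise in grade or seriousness after vaccination, the record would become treatment-emergent. The rule would need the date of the rise, which the single AE record does not hold. A change to the SAP alone therefore could not be programmed on existing data.

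**The case against.** The strongest reply is that the protocol already provides another route. Section 8.2.1.1 makes clinically significant worsening of a pre-existing condition an adverse event. Section 8.2.3.2 describes pre-existing conditions as those present on Day 0 with onset before vaccination, and sends them to baseline history. Medical history is taken again before the injection on Day 0 (Protocol Table 2). A site that follows these sections could enter the worsening as a new event with a post-vaccination onset, and nothing would be lost. This stands as a competing reading. It does not settle the matter, because an event already entered as an AE after consent also falls under 8.2.2 and 8.2.3.1, which point the other way.

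A reader might infer that a worsened event vanishes from the safety results altogether, for example a headache that reaches Grade 3 on Day 3 or a rise in ALT. The documents do not support that. The headache appears in the worst-reaction summary, and Grade 3 or higher reactions are a named part of the primary endpoint. The ALT rise appears in the chemistry shift table if it is present at a scheduled visit. Serious events stay in Table 14.3.2.1, and the protocol requires narratives for SAEs and AESIs (10.2.2.6.1).

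It is also fair to say that, with 5 to 15 participants per cohort, listings will be read closely. But Listing 16.2.7 cannot show whether the stored grade was reached before or after vaccination.

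Finally, other rules in SAP 10.8.1 lean towards counting more. Undeterminable onset dates are taken as treatment-emergent, and so are all Day 0 events, because time is not collected. A net bias of the tables is therefore not established. What remains is that this particular rule removes events and never adds any.

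**Conclusion.** The point holds for unsolicited AEs recorded in screening that worsen after vaccination, and for solicited-type symptoms that worsen after Day 3. As written, the rules leave them out of Tables 14.3.1.2 to 14.3.1.5 and out of four kinds of row in Table 14.3.1.1, and leave the SAE rows undecided.

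This assumes that sites keep one record, as 8.2.3.1 directs, for an event already on the AE form. The number of such events cannot be derived from the documents and may be small. Moderate or severe acute illness at the time of vaccination is a contraindication (Protocol 4.3.1.1), and eligibility is re-checked on Day 0 (6.2), which narrows the pool. The figures of 20.0, 16.7 and 6.7 points are the effect of one participant, not an expected bias.

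A reader might take the length of screening as the size of the problem: 42 of 42 + 28 = 70 days of unsolicited AE collection precede vaccination. That is the longest possible window, not an event rate. Nor is every event that spans Day 0 affected; only those that later worsen or become serious are.

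The change is worth making because it corrects a stated rule for a primary-endpoint table at little cost.

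**What to change.** 1. **SAP 10.8.1 and the table and listing footnotes.** Define a TEAE as an event that begins on the vaccination date or later, or that begins earlier and increases in severity or seriousness from that date onward. Record the change in SAP Section 11.
2. **Protocol 8.2.3.1 or the eCRF guideline.** Reconcile 8.2.1.1 and 8.2.3.2 with 8.2.2 and 8.2.3.1 by stating that post-vaccination worsening of an AE with earlier onset is entered as a new record dated from the worsening.
3. **Participants already enrolled.** Before or at the data review meeting (SAP Section 9), check source data for every AE ongoing at Day 0 and flag those that worsened or became serious afterwards. This step is essential, because existing AE records hold no date of worsening.
4. **Table 14.3.1.1.** State whether the SAE and related-SAE rows are restricted to treatment-emergent events.

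The cost is a few sentences of text and a short source review. Reported TEAE incidence may become slightly higher.
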